## 8.2 Statistical Analysis

### Analysis of Primary Endpoint

For Part 1 and Part 2, pharmacokinetic parameters including half-life, apparent volume of distribution\*, total clearance\*, renal clearance, net reabsorptive or secretory clearance, absorption rate constant,  $K_a$ , and  $AUC_{po}$  of thiamine and the respective SLC19A3 inhibitor will be calculated from plasma and urine drug and vitamin levels by standard pharmacokinetic methods using WinNonlin (\*these parameters are divided by bioavailability as oral doses are given). We will estimate glomerular filtration rate, GFR, using standard methods described in our previous studies. To assess net secretory or reabsorptive clearance of the compounds, we will subtract  $fu^*GFR$  (where  $fu$  is the unbound fraction of metformin, thiamine, TMP or TPP) from renal clearance of the compounds directly measured from plasma and urine values. Previously we have used these methods to calculate net secretion (or reabsorption) of several drugs. In addition, for TMP and TPP, half-life,  $AUC_{po}$ , renal clearances, net reabsorptive or secretory clearance, and ratios of AUCs of TMP and TPP to thiamine will be calculated using standard pharmacokinetic methods for metabolites.

For statistical analysis, we will use paired-t-tests to compare the pharmacokinetic parameters of thiamine in the absence and presence of an SLC19A3 inhibitor. In the pharmacokinetic analyses, we expect to see a significant influence of the SLC19A3 inhibitor on the oral exposure to thiamine,  $AUC_{po}$ . Because SLC19A3 in the proximal tubule mediates reabsorption of thiamine, we may also observe an increase in the renal clearance (reduction in reabsorptive clearance) of thiamine when volunteers are dosed with an SLC19A3 inhibitor. Understanding the effect of metformin and/or trimethoprim on renal clearance of thiamine is also of interest and could potentially contribute to even lower plasma thiamine levels.

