### Analysis of Secondary Endpoint

For the metabolic signatures, results will be processed with pair-wise mean testing, hierarchical cluster analyses, and multivariate discriminant analyses while employing multiple comparison corrections, as appropriate. Basal thiamine status including transketolase activity will be evaluated as a covariate prior to all analyses. Our primary analyses will focus on comparing the levels of the individual metabolites and metabolite ratios after vitamin administration with the baseline levels to determine if there are effects of the vitamin on the metabolite levels and ratios in the plasma. The primary comparison will test differences between treatments using one-way ANOVA with Holm-Sidak post hoc comparison, or Student's t-Tests with the False Discovery Rates adjustment of Benjamini and Hochberg. For Part 1 and Part 2, our second comparison will be to compare the levels of metabolites after thiamine administration with their levels after thiamine plus SLC19A3 inhibitor administration at multiple time points. To identify discriminants of thiamine vs. thiamine + SLC19A3 inhibitor exposure, all variables will be transformed to normality and subjected to orthogonal partial least squares – discriminant analysis (OPLS-DA) and boot strapped models will be built with a 3:1 training/test set splits using the imDEV v 1.4.268. Variables with variable importance in projection (VIP) scores <1 will be removed from further consideration, and models refined to minimize the root-mean-squared-error of prediction (RMSEP) and maximize Q2, a measure of model performance. The retained variable set will be organized using hierarchical cluster analysis. To test for significance of discriminant variables of thiamine or SLC19A3 inhibitor effects, including levels of metabolites or metabolic ratios, we will compare levels of retained metabolites (or ratios) at each time after vitamin or drug administration with baseline values, using paired-t- tests, and among times and treatments using two-way ANOVAs with Holm-Sidak post hoc comparison. To assess covariate behavior among thiamine, TPP, metformin, other metabolites and/or or metabolite ratios, hierarchical cluster

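### On the natural reading, treatment tests on VIP-retained metabolites reuse the contrast and data that selected them; one VIP pass raises null rejections about two- to threefold

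*Combined protocol and SAP*

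**What the plan says.** Section 8.2, Analysis of Secondary Endpoint, sets out these steps.

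- **Full-set comparisons.** "The primary comparison will test differences between treatments using one-way ANOVA with Holm-Sidak post hoc comparison", with Student's t-tests under Benjamini-Hochberg as the alternative. A second comparison sets metabolite levels after thiamine against "levels after thiamine plus SLC19A3 inhibitor administration at multiple time points". Neither is described as limited to selected variables, and no pairing is stated for either.
- **Selection.** OPLS-DA is fitted for this purpose: "To identify discriminants of thiamine vs. thiamine + SLC19A3 inhibitor exposure". Bootstrapped models are built with 3:1 training/test splits. Variables with VIP below 1 "will be removed from further consideration, and models refined to minimize the root-mean-squared-error of prediction (RMSEP) and maximize Q2".
- **Tests on what is left.** "To test for significance of discriminant variables of thiamine or SLC19A3 inhibitor effects", the plan says "we will compare levels of retained metabolites (or ratios) at each time after vitamin or drug administration with baseline values" by paired t-tests, and "among times and treatments using two-way ANOVAs with Holm-Sidak post hoc comparison".

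Corrections for multiple comparisons are promised where appropriate, but no family of tests is defined. The section gives no alpha, no number of metabolites, no number of metabolomic time points and no treatment of subject in the ANOVAs. For the pharmacokinetic parameters, by contrast, pairing is explicit: "we will use paired-t-tests to compare the pharmacokinetic parameters of thiamine in the absence and presence of an SLC19A3 inhibitor".

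**The concern.** VIP ranks variables by their association with the treatment label. Testing the top-ranked variables for a difference between those same treatments, on the same samples, gives p-values that are conditional on having already looked promising. Holm-Sidak across times and treatments within one metabolite does not correct for having screened metabolites on that contrast.

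The secondary objective in both parts (section 3) is to find metabolites that might serve as signatures of reduced thiamine absorption. If significance is read from the retained-set treatment tests, more of the candidates will be false than the p-values imply. The consequence is confined to which metabolites are carried forward.

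**Working it through.** The plan gives no error rate for this analysis, so there is no figure to reproduce.

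**Inputs from the documents:** 6 completers in Part 1 and 12 in Part 2 (section 8.3); 14 and 13 post-dose pharmacokinetic draws (section 5.1), used only as upper values, because section 5.3 ties the draws to thiamine, its phosphate esters and the two inhibitors.

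**Assumptions:** two-sided alpha 0.05; two arms; 30 or 100 metabolites; between-metabolite correlation 0, 0.3 or 0.6; 2, 4, 8 or 13–14 metabolomic times; subject / subject-by-cycle variance of 30/0, 30/5, 30/10, 30/20 or 50/0% of the total.

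**Analytic check.** For one predictive component, VIP_j = √p·|w_j|/‖w‖ with w = X′y on autoscaled data. VIP_j ≥ 1 then means that w_j² is at or above its average. For independent null metabolites w_j² behaves like a scaled chi-square on 1 df, so the retained share is P(χ²₁ > 1) = 0.317. Every variable with p<0.05 (χ² > 3.84) is among those retained. The share with p<0.05 therefore becomes 0.05/0.317 = 0.158, and 0.158/0.05 is about 3.15-fold.

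**Simulation under a global null.** 240 settings, 1,000 datasets each, one VIP pass; 31–36% of metabolites kept. Share with p<0.05:

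| Test | All | Retained | Ratio |
|---|---|---|---|
| Paired t on subject means (illustration) | 4–6% | 11–16% | 2.3–3.1 |
| Two-way ANOVA treatment effect, no subject term | 1–30% | 2–87% | 2.3–3.2 |
| Same, with subject term | 4–41% | 12–99% | 2.1–3.2 |
| Any Holm-Sidak time-specific treatment contrast | 0.2–2.5% | 0.3–6.8% | 1.4–3.0 |

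A second simulation on other assumptions gave 1.9–3.2 for the ANOVA and 2.4–3.2 for the paired test. A three-treatment Part 1 version gave 2.2–2.6.

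**Is reuse the cause?** Selecting on 75% of subjects and testing on all still gave 2.0–3.2. Selecting in half the subjects and testing in the other half gave 0.92–1.03 (4.6–5.2% among retained against 4.8–5.2% overall). The effect disappears when the data are separate.

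**Sensitivity to the VIP definition (paired-test ratio).**

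- Averaged over 3:1 resamples: 2.8–4.3.
- Averaged over bootstraps: 3.2–5.3.
- One further removal round: 4.0–7.5, and about 6–9 in the second simulation.
- Ordinary two-component PLS: 2.7–3.0 at correlation 0, 1.1–1.8 at 0.3, and 0.7–1.0 (no inflation) at 0.6.

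**Selection versus pseudo-replication.** At 30/10% variance the ANOVA without a subject term rejects 9–10% of retained nulls with 2 times, 14–18% with 4, 25–32% with 8 and 39–54% with 13–14. The selection ratio stays at 2.3–3.2, so the climb comes from treating repeated samples as independent.

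**Consequence for discovery.** With Benjamini-Hochberg on the paired test, at least one false positive occurs in 3–7% of null trials over the full set and 7–19% over the retained set. With 10% of 100 metabolites truly affected (0.3 or 0.6 SD), the true false discovery rate is 3–6% over the full set and 7.5–20% over the retained set.

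**Baseline comparison.** Within an arm, post-dose minus baseline shares post-dose noise with the selecting contrast. Retained-set rejections rise 1.5–1.7-fold with one post-dose time, 1.2–1.3-fold with two, and stay near 1 (at most about 1.2) with four or more.

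**The case against.** **The plan does have a split, and does not say that the tests reuse the training data.** True: reuse is inferred. But the split is attached only to building the models, and nothing sends the later tests to a held-out part or commits to selecting in Part 1 and testing in Part 2. A reader might infer that the plan openly declares the reuse. It does not; the accurate statement is that no separate data are named.

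**The quoted Holm-Sidak contrasts show little absolute harm.** This stands in part: 0.3–6.8% among retained nulls is at most slightly above 5%. But the low level comes from leaving subject variance in the error term. With 30% subject variance and no subject-by-cycle variance, the cut-off 1.96 acts like 1.96/√0.7 = 2.34, so a nominal 5% is about 1.9% before selection. The proportional rise remains, and the ANOVA treatment effect has no such cushion once subject is modelled.

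**Much of the remedy is already planned.** Also partly true: the full-set comparison carries a multiplicity adjustment and escapes selection. But it has no stated pairing, and it is the retained-set tests that the plan describes as testing significance.

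**This is discovery work.** Accepted, and it limits the weight of the point. It does not make an invalid p-value valid.

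**Conclusion.** The point holds for the treatment tests on the retained set. With one VIP pass on the predictive component, and no separate data, null rejections rise about two- to threefold; a valid paired test goes from 5% to about 11–16%. This rests on the assumed alpha, metabolite number and correlation, and variance shares listed above. The multiplier is not universal: it can vanish for multi-component VIP with highly correlated metabolites, and reach 3–7 or more with bootstrap averaging or a second removal round. The plan does not say how VIP is aggregated over the bootstrapped models, or whether refinement drops variables again.

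Three stronger readings are not supported.

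- A reader might take the 87–99% rates as the effect of selection. Those ANOVAs already rejected up to 30% and 41% of nulls before selection, because repeated samples were treated as independent. The ANOVA's absolute rate cannot be derived from the plan, which leaves the subject term, the number of times and the variance components open.
- A reader might extend the problem in full to the baseline comparison. That test is only slightly affected when several times are used.
- A reader might extend it to the primary endpoint. The AUC test involves no such selection.

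This should be corrected, as a matter of secondary discovery analysis.

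**What to change.** In section 8.2, state that significance claims for the inhibitor effect rest on the full-set comparison of thiamine with thiamine plus inhibitor. Specify it as a paired test on a subject-by-cycle summary, or an equivalent mixed model with subject and subject-by-cycle terms, with Benjamini-Hochberg over all measured metabolites and ratios. Name the metabolomic time points. Pairing has to be written in: at 30/10% variance an unpaired one-way ANOVA on pooled samples rejects 3–4% of full-set nulls with 2 times but 16–19% with 13–14, and at 50/0% only 0.7–1.4%.

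Use VIP and the retained-set tests to rank and describe. If retained-set p-values are wanted, repeat the VIP selection inside a within-subject permutation of treatment labels. In simulation (400 null datasets, 50 metabolites, 4 times, correlation 0.3, 30/10% variance) this gave a 3.5% (6 subjects) and 3.3% (12 subjects) chance of any false discovery, against 14.5% and 11.5% with Benjamini-Hochberg on the retained set.

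The cost is SAP wording and code, plus fewer nominal discoveries. For 0.6 SD effects (30/10% variance, 100 metabolites), power per metabolite for the paired full-set analysis against the invalid retained-set one is:

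- 12 subjects, 13 times: 54% against 87%.
- 12 subjects, 4 times: 18–20% against 51–52%.
- 6 subjects, 14 times: 4% against 19–20%.

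With 6 completers there are 2⁶ = 64 label swaps, so a two-sided permutation p cannot fall below 2/64 = 0.031. Part 1 metabolomics would be mainly descriptive, and the plan should say so.

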analyses will be performed and Spearman's correlation matrices will be generated. Linear correlation analyses will be conducted, and correlation coefficients will be estimated for each metabolite in each volunteer (in each study arm). To compare time-dependent changes in each study arm, in addition to our pharmacokinetic analysis, plasma thiamine will first be modeled as a continuous variable using partial least squares discriminant analysis, and variables with variable importance in projection scores (VIP) >1 will be selected. The average metabolite value will then be independently calculated in each study arm, and variables will be organized in the self-organizing maps using the Kohonen package in R70. Patterns will be compared between treatment groups by regression analysis of representative variable group members. Additional complex relationships will be examined if the data warrant those, for example, Emax models may be used to characterize the relationship between thiamine levels and levels of metabolites or metabolic ratios.

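### A VIP cut of 1 always returns a set of metabolites, and the plasma-thiamine model passes that set to maps without a check against chance

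*Combined protocol and SAP*

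**What the plan says.** Section 8.2, Analysis of Secondary Endpoint, uses a VIP cut of 1 in two multivariate models.

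- **Treatment model** (OPLS-DA, thiamine alone against thiamine plus inhibitor). "Variables with variable importance in projection (VIP) scores <1 will be removed from further consideration". The plan adds that "boot strapped models will be built with a 3:1 training/test set splits" and wants "models refined to minimize the root-mean-squared-error of prediction (RMSEP) and maximize Q2, a measure of model performance". Significance tests follow: "we will compare levels of retained metabolites (or ratios) at each time after vitamin or drug administration with baseline values", by paired t-test, and two-way ANOVA across times and treatments with Holm-Sidak adjustment.
- **Thiamine model.** Here the response is continuous: "plasma thiamine will first be modeled as a continuous variable using partial least squares discriminant analysis". The selection rule applied to that fit is that "variables with variable importance in projection scores (VIP) >1 will be selected". Arm averages are then calculated and "variables will be organized in the self-organizing maps using the Kohonen package". A regression of representative group members then compares patterns between treatment groups.

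The same section plans a univariate comparison between treatments, adjusted by Holm-Sidak or by the Benjamini-Hochberg false discovery rate, which does not use VIP. It also plans Spearman matrices and per-volunteer linear correlations, described before the thiamine model. The number of metabolites, the number of components and any minimum Q² are not given. Section 8.3 plans six completers in Part 1 and twelve in Part 2.

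**The concern.** A selection rule that is to yield biomarkers should be able to come back empty when nothing is there. VIP >1 cannot: it asks only whether a variable matters more than the average variable in the fitted model, even if that model describes noise.

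The exposure is greatest in the thiamine model. The plan states no hold-out, no Q² criterion and no permutation test for it before the maps are built. If no metabolite tracked thiamine, this branch would still deliver a selected set and a map. Section 3 hopes that the secondary analysis will lead to biomarkers of reduced thiamine absorption, so such a set could be taken for a finding. With six or twelve volunteers, noise alone can produce convincing patterns. The primary AUC comparison is not affected.

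**Working it through.** The plan states no selection rate, error rate or power for this analysis, so there is no figure to reproduce.

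**1. The cut taken alone.** The plan gives no VIP formula; I use the standard one. With p variables, unit-norm weights w_ja and SS_a the response variation explained by component a:

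VIP_j² = p · Σ_a (SS_a · w_ja²) / Σ_a SS_a

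Sum over j. Since Σ_j w_ja² = 1 for each component, Σ_j VIP_j² = p, and the mean of VIP² is exactly 1. Unless every VIP equals 1, at least one exceeds it. No property of the data enters.

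**2. Share kept when nothing is associated.** With one component and independent variables, VIP_j² behaves like a chi-square on 1 degree of freedom, so the share is P(|Z| > 1) = 2 × (1 − Φ(1)) = 31.7%.

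Simulation with assumed inputs (30, 100 or 300 variables; independent, block-correlated at 0.8, or equicorrelated at 0.5 or 0.9; 12, 24, 36 or 168 samples; 1 to 3 components; 300 data sets per setting):

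- averages by setting: 31.9% to 41.4%
- single data sets, 2.5th to 97.5th percentiles: mostly 20% to 57%
- lowest single share: 10%; never zero

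A second simulation (6, 12 or 18 volunteers; five common factors carrying 60% of the variance; within-volunteer correlation 0.5) gave treatment-model averages of 33% to 42%. With continuous thiamine unrelated to any of 100 metabolites and one component, 34% to 36% were kept, never fewer than 25%.

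**3. Share kept when something is associated.** With 24 samples, 100 variables and one component, the average was 24% when 10 variables were shifted by 2 SD and 49% when 50 were. The number retained therefore does not tell signal from noise: the first case keeps fewer variables than the null does.

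**4. What follows the cut in the treatment model.** Null data, 12 pairs, 100 variables, one component, 2,000 runs. About 32 variables were kept (fewest 21).

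| Test of retained variables | Runs with at least one false finding |
|---|---|
| Unadjusted paired p < 0.05 | 99.6% |
| Holm-Sidak over retained variables only | 16.4% |
| Benjamini-Hochberg over retained variables only | 17.4% |
| Holm-Sidak over all 100 | 5.4% |
| Benjamini-Hochberg over all 100 | 5.5% |

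So if the adjustment runs across metabolites, this branch returns nothing in about 83% of null runs (100 − 16.4 = 83.6; 100 − 17.4 = 82.6). Adjusting over retained variables only makes the error about three times as large (16.4 / 5.4 = 3.0). The plan ties Holm-Sidak to times and treatments; whether it also covers metabolites is unclear.

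**5. Q² as a guard.** In 300 null runs, cross-validated Q² exceeded 0 in 8% when all variables were used and in 99% when VIP selection was done outside the cross-validation. Q² is informative only if selection is nested in the splits, which the plan does not state.

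**6. A permutation gate on Q².** With selection nested, whole volunteers held out and treatment labels swapped within volunteer, the gate was passed in 3 to 5% of null trials. For a 1-SD effect on 10 of 100 metabolites it was passed in about 98% of trials with 12 volunteers and about 30% with 6. Part of the loss at 6 is arithmetic. A two-treatment comparison has 2⁶ = 64 label swaps; reversing every label leaves Q² unchanged, so there are 64 / 2 = 32 distinct arrangements. The two smallest attainable p-values are 1/32 = 0.031 and 2/32 = 0.063, so only the single best arrangement can pass at 5%.

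**The case against.** A reader might infer that the plan always keeps about a third of the metabolites and can never report that it found no signature. The documents do not support either statement.

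- **The share is not fixed.** It depends on components, correlation and signal, as steps 2 and 3 show.
- **In the treatment model the VIP cut is a filter, not a verdict.** Training/test splits, RMSEP and Q², and significance tests come after it and can end in a null result. Q² also has a natural reference point: zero means no better than predicting the mean.
- **The adjusted univariate comparison** bypasses VIP, directly serves the objective of comparing metabolite levels, and can return nothing.
- **The thiamine model can be read as descriptive**, a way of organising time courses by arm in a discovery analysis.

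These points stand and limit the claim. They do not close the gap. The planned correlations carry no decision rule tied to selection. The regression after the maps compares treatment groups; it does not test whether the selected metabolites track thiamine. The plan does not label the maps descriptive. In the treatment model the guards are weak as written, because Q² is only to be maximised, nesting is not stated, and the tests cover retained variables only.

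A fair objection to the remedy is its power: with six volunteers a gate will often miss a real effect. That also stands, and determines how a failed gate may be reported.

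**Conclusion.** The concern holds in limited form. That the VIP cut alone always returns a set follows from algebra and needs no assumption about the data, only the standard VIP definition. The size, roughly 32 to 42% of variables on average under no association, rests on assumed metabolite numbers and correlations, with PLS standing in for OPLS-DA.

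The gap is clearest in the thiamine model, where nothing tests the model before its output is mapped. In the treatment model it is partial: a null result is possible, but no Q² criterion or nested selection protects against a favourable result from noise. It would be wrong to conclude that the whole secondary analysis is unable to report a null finding. This is a secondary, discovery-oriented analysis, and the correction should be made before the metabolite data are analysed.

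**What to change.** Add one paragraph to Section 8.2, applying before any VIP-selected set is interpreted as a signature or passed to the maps:

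1. Compute Q² with whole volunteers held out, repeating VIP selection and refinement inside each training set.
2. Repeat the entire procedure on permuted data. For the OPLS-DA, swap treatment labels within volunteer, keeping all samples of a cycle together. For the thiamine model, reassign whole thiamine time profiles between volunteers within an arm, and note that this tests volunteer-specific tracking beyond the time course that volunteers share.
3. Interpret the VIP-selected set only if the observed Q² exceeds the 95th percentile of the permuted values. In Part 1, enumerate the label swaps rather than sampling them.
4. Otherwise report that no signature was demonstrated, and label any VIP list or map as descriptive ranking only.
5. Leave the adjusted univariate comparisons in place whatever the gate shows.

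The cost is the paragraph and some computing time; no new data are needed. The real downside is low power in Part 1: about 30% for the effect simulated above, so about 70% of such effects would be missed (100 − 30). The text should say that a failed gate in Part 1 is inconclusive and is not evidence of no effect.
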